9.1. Schedule of Study Assessments

		Day	Day	Week	Week	Week	Week	Week	Week	Week	Week	Week	Week	Week	Week	Week
Assessments	Screening	0	1	 2	4	6	8	10	12	14	16	18	20	22	24	26
		-5 to														
		0		±5	±5	±5	±5	±5	±5	±5	±5	±5	±5	±5	±5	±5
Visit Window (Days)	-28 to 0	days		days	days	days	days	days	days	days	days	days	days	days	days	days
Informed																
Consent/Assent*	Х															
Inclusion/Exclusion																
Criteria	х															
Medical History																
(review of changes																
from NGLU-CL01)	х															
Physical Examination	Х	XP	Х		X ^P		X ^P		XP		X ^P		XP		X ^P	
Height and Weight	х	X ^P			X ^P		XP		XP		X ^P		XP		X ^P	
Vital Signs	х	х	х	х	х	х	х	х	х	х	х	х	х	х	х	х
12-lead ECG																
(Triplicate)	х	X ^P							XP						X ^P	
FDNA	Х														х	
Vineland-II, BSID-III,																
KABC-II, BOT-2																
Brief Form, CCC-2,																
SBRS,CSHQ, ZBI, SF-																
10 ²	Х			 											X ^p	
Haematology, Serum																
Chemistry (including																
Coagulation),																
Urinalysis ³	Х	X	Х		X ^P		X ^P		X		X ^P		X		X	
Pregnancy Test (Urine) ⁴	x	XP			X ^P		XP		XP		XP		XP		XP	

Alexion Pharmaceuticals, Inc. {Protocol: NGLU-CL01-T 24 Feb 2016 (Version 2.0 Final)}

Statistical Analysis Plan {01 Sep 2017, Version 1.0}

	Companying a	Day	Day	Week	Week	Week	Week	Week	Week	Week	Week	Week	Week	Week	Week	Week
Assessments	Screening	0	1	2	4	6	8	10	12	14	16	18	20	22	24	26
		-5 to		_	_	_	_	_	_	_	_	_	_	_	_	_
		0		±5	±5	±5	±5	±5	±5	±5	±5	±5	±5	±5	±5	±5
Visit Window (Days)	-28 to 0	days		days	days	days	days	days	days	days	days	days	days	days	days	days
Serum and Urine																
Heparan Sulphate																
(Total and NRE)	х	X ^P			XP		XP		XP		XP		XP		X ^P	
Serum Ferritin and																
Chitotriosidase	х	XP			XP		XP		XP		XP		X ^P		X ^P	
Plasma Glutamic Acid																
and Glycine	х	XP			XP		XP		XP		XP		XP		XP	
NAGLU enzyme																
activity	x															
Serum Biomarkers																
(Exploratory including																
IgG inflammatory																
markers)		XP			XP		XP		XP		XP		XP		XP	
Serum																
Pharmacokinetic																
Profile ⁵		x							х						х	
SBC-103 ADA ⁶		XP			XP		X ^P		XP		XP		X ^P		XP	
General																
Anaesthesia/Sedation ⁷		XP							XP						XP	
Lumbar Puncture ^{7,8}		X ^P							X ^P						XP	
Heparan Sulphate																
(Total and NRE) in																
CSF		XP							XP						XP	
Calbindin D. HGF. Tau.																
pTau, Amyloid β,																
Albumin, IgG in CSF		XP							XP						X ^P	
Glutamic Acids and			-													
Glycine in CSF		XP							X ^P						X ^P	

Alexion Pharmaceuticals, Inc. {Protocol: NGLU-CL01-T 24 Feb 2016 (Version 2.0 Final)}

Statistical Analysis Plan {01 Sep 2017, Version 1.0}

		Day	Day	Week	Week	Week	Week	Week	Week	Week	Week	Week	Week	Week	Week	Week
Assessments	Screening	0	1	2	4	6	8	10	12	14	16	18	20	22	24	26
		-5 to														
		0		±5	±5	±5	±5	±5	±5	±5	±5	±5	±5	±5	±5	±5
Visit Window (Days)	-28 to 0	days		days	days	days	days	days	days	days	days	days	days	days	days	days
Routine Findings																
(Cell Counts, Glucose, Protein) in CSF ³		X ^P							X٩						X ^P	
SBC-103 in CSF		X ^P							X ^P						X ^P	
Structural and Diffusion MRI ⁷		XP													X٩	
Telephone call				х	х	х										
SBC-103 Dosing		х		х	х	х	х	х	х	х	х	х	х	х	х	х
Adverse Events ¹⁰		CONTINUOUS														
Concomitant Medications ¹¹	CONTINUOUS															

	Week	Week	Week										
Assessments	28	30	32	34	36	38	40	42	44	46	48	50	52
Visit Window (Days)	±5 davs	±5 davs	±5 davs	±5 davs	±5 davs	±5 davs	±5 davs	±5 davs	±5 days	±5 davs	±5 davs	±5 davs	±5 davs
Physical Examination	v ^p	uays	v ^p										
Hoight and Woight	A VP		A VP										
Vital Signs	~		×		~		×		~		×		×
	X	X	X	X	X	X	X	X	X	X	X	X	X
12-lead ECG													X'
FDNA													Х
Vineland-II, BSID-III, KABC-II, BOT-2 Brief Form, CSHQ, CCC-2, SBRS, ZBL SF-10 ²													X ^P
Haematology, Serum													
Chemistry (incl. Coagulation), Urinalysis ³	XP				X ^P				XP				XP
Pregnancy Test (Urine) ⁴	X ^P		X ^P										
Serum and Urine Heparan Sulphate (Total and NRE)	X ^P				X٩				X ^P				X ^P
Serum Ferritin and Chitotriosidase	X ^P				X				X ^P				X۶
Plasma Glutamic Acid and Glycine	X ^P				X				X ^P				X۶
Serum Biomarkers (Exploratory including IgG, inflammatory markers)	X ^P				X ^P				X ^P				X ^P
Serum Pharmacokinetic Profile⁵													x
SBC-103 ADA ⁶	XP		X ^P		X ^P		X ^p		XP		X ^P		X ^P
General Anaesthesia/Sedation ⁷					XP								XP

Assessments	Week 28	Week 30	Week 32	Week 34	Week 36	Week	Week 40	Week 42	Week 44	Week 46	Week 48	Week 50	Week
				• ·									
	±5	±5	±5	±5	±5	±5	±5	±5	±5	±5	±5	±5	±5
Visit Window (Days)	days	days	days	days	days	days	days	days	days	days	days	days	days
Lumbar Puncture ^{7,8}	-				X ^p								X ^P
Heparan Sulphate (Total and					X ^p								
NRE) in CSF													X ^P
Calbindin D, HGF, Tau,					X ^P								
pTau, Amyloid β, Albumin,													
IgG in CSF													X ^P
Glutamic Acids and Glycine					X ^p								
in CSF													XP
Routine Findings (Cell					X ^P								
Counts, Glucose, Protein) in													
CSF ³													XP
SBC-103 in CSF					XP								X ^P
Structural and Diffusion													
MRI ⁷													X ^P
SBC-103 Dosing	х	х	х	х	х	х	х	х	х	х	х	х	х
Adverse Events ¹⁰	CONTINUOUS												
Concomitant Medications ¹¹							CONTINUOUS	5					

Accessments	Week	Week	Week										
Assessments	54	56	58	60	62	64	66	68	70	12	74	76	/8
	±5	±5	±5	±5	±5	±5	±5	±5	±5	±5	±5	±5	±5
Visit Window (Days)	days	days	days										
Physical Examination		X ^p											
Height and Weight		X ^P											
Vital Signs ¹²	Х	Х	х	х	х	х	Х	х	Х	Х	х	х	Х
12-lead ECG ¹													X ^P
FDNA													Х
Vineland-II, BSID-III, KABC-II, BOT-2 Brief Form, CSHQ, CCC-2, SBRS, ZBI, SF-10 ²													X ^P
Haematology, Serum Chemistry (including Coagulation), Urinalysis ³				X ^p				X٩					X ^P
Pregnancy Test (Urine) ⁴		X ^P		X۶		X٩		X ^P		X ^P		X٩	
Serum and Urine Heparan Sulphate (Total and NRE)				X				X ^p					Xp
Serum Ferritin and Chitotriosidase				X۶				X ^P					X ^P
Plasma Glutamic Acid and Glycine				X۶				X ^P					X ^P
Serum Biomarkers (Exploratory including IgG, inflammatory markers)				X ^p				X ^P					X ^P

Proprietary and Confidential

Page 26 of 37

Statistical Analysis Plan {01 Sep 2017, Version 1.0}

Assessments	Week	Week	Week	Week	Week	Week 64	Week 66	Week	Week 70	Week 72	Week 74	Week 76	Week 78
	54	50	50		02					/2	74		/0
	±5	±5	±5	±5	±5	±5	±5	±5	±5	±5	±5	±5	±5
Visit Window (Days)	days	days	days	days	days	days	days	days	days	days	days	days	days
Serum Pharmacokinetic Profile⁵													х
SBC-103 ADA ⁶		X ^P		X ^P		X ^P		X ^P		X ^P		X ^P	
General Anaesthesia/Sedation ⁷								X ^P					X ^P
Lumbar Puncture ^{7,8}								X ^P					XP
Heparan Sulphate (Total and NRE) in CSF								X ^P					X ^P
Calbindin D, HGF, Tau, pTau, Amyloid β, Albumin, IgG in CSF								X ^p					X ^P
Glutamic Acids and Glycine in CSF								X ^P					X ^P
Routine Findings (Cell Counts, Glucose, Protein) in CSF ³								X ^P					X ^P
SBC-103 in CSF								X ^p					XP
SBC-103 Dosing	Х	Х	Х	х	Х	х	х	х	Х	Х	х	х	Х
Adverse Events ¹⁰							CONTINUOU	S					
Concomitant Medications ¹¹		CONTINUOUS											

	Week	Week	Week	Week	Week	Week	Week	Week	Week	Week	Week	Week	Week
Assessments	80	82	84	86	88	90	92	94	96	98	100	102	104
	±5	±5	±5	±5	±5	±5	±5	±5	±5	±5	±5	±5	±5
Visit Window (Days)	days	days	days	days	days	days	days	days	days	days	days	days	days
Physical Examination	X ^P		X ^P		X ^P		X ^P		XP		X ^P		XP
Height and Weight	X ^P		X ^P		X ^P		X ^p		X ^p		X ^P		X ^P
Vital Signs ¹²	х	х	х	х	х	х	х	х	х	х	х	х	х
12-lead ECG ¹													X ^P
FDNA													х
Vineland-II, BSID-III, KABC-II, BOT-2 Brief Form, CSHQ, CCC-2, SBRS, ZBI, SF-10 ²													X ^p
Haematology, Serum Chemistry (including Coagulation), Urinalysis ³				X ^p				X ^p					X ^P
Serum albumin sample						XP							
Pregnancy Test (Urine) ⁴	XP		X٩		XP		X ^P		X ^P		X ^P		X ^P
Serum and Urine Heparan Sulphate (Total and NRE)				X ^P		X ^P		X ^P					X ^p
Serum Ferritin and Chitotriosidase				X٩				X ^P					X ^P
Plasma Glutamic Acid and Glycine				X ^P				X ^P					X ^P
Serum Biomarkers (Exploratory including IgG, inflammatory markers)				X ^p				X ^p					X ^P

Proprietary and Confidential

Assassments	Week	Week	Week	Week	Week	Week	Week	Week	Week	Week	Week	Week	Week
Assessments	80	02	04	80	00	90	92	54	90	30	100	102	104
	+5	+5	+5	+5	+5	+5	+5	+5	+5	+5	+5	+5	+5
Visit Window (Davs)	davs	davs	davs	davs	davs	davs	davs	davs	davs	davs	davs	davs	davs
Serum Pharmacokinetic Profile ⁵													x
SBC-103 ADA ⁶	X ^P		X ^P		X ^P		XP		XP		X ^P		X ^P
General Anaesthesia/Sedation ⁷						X٩							X ^P
Lumbar Puncture ^{7,8}						X ^P							XP
Heparan Sulphate (Total and NRE) in						X ^p							Xp
Calbindin D. HGF. Tau.						~							~
pTau, Amyloid β , Albumin, IgG in CSF						XP							X ^P
Glutamic Acids and Glycine in CSF						X۶							XP
Routine Findings (Cell Counts, Glucose, Protein) in CSF ³						X ^P							X ^p
SBC-103 in CSF						XP							XP
Structural and Diffusion MRI ⁷													XP
SBC-103 Dosing	Х	х	х	х	х	х	х	х	х	х	х	х	х
Adverse Events ¹⁰							CONTINUOU	S					
Concomitant Medications ¹¹							CONTINUOU	S					

Assessments	Week 106	Week 108	Week 110	Week 112	Week 114	Week 116	Week 118	Week 120	Week 122	Week 124	Week 126	Week 128	Week 130	Week 132
	±5	±5	±5	±5	±5	±5	±5	±5	±5	±5	±5	±5	±5	±5
Visit Window (Days)	days	days	days	days										
Physical Examination		X ^P		XP										
Height and Weight		X ^P		X ^P										
Vital Signs ¹²	х	Х	Х	х	Х	Х	Х	Х	Х	Х	Х	х	х	х
12-lead ECG ¹													XP	
FDNA													х	
Vineland-II, BSID-III, KABC-II, BOT-2 Brief Form, CSHQ, CCC-2,													XP	
SBRS, ZBI, SF-10 ²			 											
Chemistry (including				X ^P				X ^P					X ^P	
Pregnancy Test (Urine) ⁴		XP	1	XP	1	XP								
Serum and Urine Heparan Sulphate (Total and NRE)				X ^P				XP					XP	
Serum Ferritin and Chitotriosidase				XP				XP					X ^P	
Plasma Glutamic Acid and Glycine				X ^P				X ^P					X ^P	
Serum Biomarkers (Exploratory including IgG, inflammatory markers)				X ^p				X ^p					X ^p	
Serum Pharmacokinetic Profile⁵													x	
SBC-103 ADA ⁶		XP		XP		XP		XP		X ^P	1	XP		X ^P

Proprietary and Confidential

Statistical Analysis Plan {01 Sep 2017, Version 1.0}

According	Week	Week	Week	Week	Week	Week	Week	Week						
Assessments	106	108	110	112	114	110	118	120	122	124	126	128	130	132
Vicit Window (Days)	±5	±5	±5	±5	±5	±5	±5	±5	±5	±5	±5	±5	±5	±5
visit window (Days)	days	days	days	days	days	days	days	days						
General Anaesthesia/Sedation ⁷								XP					X ^P	
Lumbar Puncture ^{7,8}								XP					X ^P	
Heparan Sulphate (Total and NRE) in CSF								X٩					X٩	
Calbindin D, HGF, Tau, pTau, Amyloid β, Albumin, IgG in CSF								X ^p					X ^P	
Glutamic Acids and Glycine in CSF								X ^P					X٩	
Routine Findings (Cell Counts, Glucose, Protein) in CSF ³								X ^P					X ^P	
SBC-103 in CSF								X ^P					X ^P	
SBC-103 Dosing	х	х	х	х	х	х	х	х	х	х	х	х	х	х
Adverse Events ¹⁰							CONTI	NUOUS						
Concomitant Medications ¹¹							CONTI	NUOUS						

	Wook	Wook	Wook	Wook	Wook	Wook	Wook	Wook	Wook	Wook	Wook	Week 156/ End of Treatment/	Week
Assessments	134	136	138	140	142	144	146	148	150	152	154	Early Termination	160
												remination	
	±5	±5	±5	±5	±5	±5	±5	±5	±5	±5	±5	±5	±5
Visit Window (Days)	days	days	days	days	days	days	days	days	days	days	days	days	days
Physical Examination		X ^P		X ^P		XP		XP		X ^P		X ^P	
Height and Weight		X ^P		XP		X ^P		X ^P		XP		X ^P	
Vital Signs ¹²	Х	х	х	х	х	Х	Х	Х	х	х	х	Х	
12-lead ECG ¹												X ^P	
FDNA												х	
Vineland-II, BSID-III, KABC-II, BOT-2 Brief Form, CSHQ, CCC-2, SBRS, ZBI, SF- 10 ²												X ^P	
Haematology, Serum Chemistry (including Coagulation), Urinalysis ³			X ^P				X ^p					X ^P	
Serum Albumin sample					х								
Pregnancy Test (Urine) ⁴		X ^P		X ^P		X ^P		XP		XP		X ^P	
Serum and Urine Heparan Sulphate (Total and NRE)			X۶		X٩		X ^P					X ^p	
Serum Ferritin and Chitotriosidase			X۶				X ^P					X ^p	
Plasma Glutamic Acid and Glycine			X۶				XP					X ^p	
Serum Biomarkers (Exploratory including IgG, inflammatory markers)			X ^p				XP					X ^P	
Serum Pharmacokinetic Profile⁵												Х	

Proprietary and Confidential

Alexion Pharmaceuticals, Inc. {Protocol: NGLU-CL01-T 24 Feb 2016 (Version 2.0 Final)}

Statistical Analysis Plan {01 Sep 2017, Version 1.0}

												Week 156/ End of	
												Treatment/	
	Week	Week	Week	Week	Week	Week	Week	Week	Week	Week	Week	Early	Week
Assessments	134	136	138	140	142	144	146	148	150	152	154	Termination	160
Visit Window (Dovs)	±5	±5	±5	±5	±5	±5	±5	±5	±5	±5	±5	±5	±5
	days	days	days	days	days	days	days	days	days	days	days	days	days
SBC-103 ADA		X.		X.		X.		X		X.		X	
General Anaesthesia/Sedation ⁷					X ^P							X ^P	
Lumbar Puncture ^{7,8}					X ^p							XP	
Heparan Sulphate (Total and NRE) in CSF					X ^P							X۶	
Calbindin D, HGF, Tau,													
pTau, Amyloid β, Albumin,					X ^P							XP	
IgG in CSF													
Glutamic Acids and Glycine					XP							XP	
in CSF					~							~	
Routine Findings (Cell													
Counts, Glucose, Protein) in CSF ³					X ^P							X ^P	
SBC-103 in CSF					XP							X ^P	
Structural and Diffusion MRI ⁷												X ^P	
Telephone call ⁹													х
SBC-103 Dosing	Х	Х	Х	Х	Х	Х	х	х	Х	х	Х	х	
Adverse Events ¹⁰		•	•	•	•	•	CONTINU	OUS	•		•		•
Concomitant Medications ¹¹							CONTINU	OUS					

Statistical Analysis Plan {01 Sep 2017, Version 1.0}

Key: ADA = anti-drug antibodies; BOT-2 Brief Form = Bruininks-Oseretsky Test of Motor Proficiency, Second Edition, Brief Form; BSID-III = Bayley Scales of Infant and Toddler Development, Third Edition; CCC-2 = Children's Communication Checklist, Second Edition; CSF = cerebrospinal fluid; CSHQ = Children's Sleep Habits Questionnaire; D = day; ECG = electrocardiogram; FDNA = Facial Dysmorphology Novel Analysis; HGF = hepatocyte growth factor; IgG = immunoglobulin G; KABC-II = Kaufman Assessment Battery for Children, Second Edition; NAGLU = alpha-N-acetylglucosaminidase; MRI = magnetic resonance imaging; NRE = non- reducing end; SBRS = Sanfilippo Behavior Rating Scale; SF-10 = Short Form Health Survey for Children; Vineland-II = Vineland Adaptive Behavior Scales, Second Edition; Wk = week; ZBI = Zarit Burden Interview, 12-item.

*All study visits will be scheduled relative to Day 0. Infusions will be administered every 14 days ± 5 days and must be administered at least 10 days apart. Informed consent may be granted before the beginning of the screening period. All screening assessments other than informed consent should be completed within a 28-day window.

- X^P Assessments to be performed pre-dose
- ¹ ECG assessments after 6 months do not need to be performed in triplicate.
- ² The Vineland-II, BSID-III or KABC-II, BOT-2 Brief Form, and CCC-2 should be administered in-person by an appropriately qualified professional.
- ³ Local lab ranges will be used for those labs analysed locally. If samples are taken within 3 days of Day 0, samples do not need to be repeated on Day 0. However, a Day 0 serum sample for albumin should be collected at the same time as the CSF collection, to enable calculation of CSF-AI. Central laboratory parameter reference ranges will be used throughout the study, including in the event that laboratory parameters are analysed locally. All attempts should be made to draw laboratory samples for central laboratory analysis when samples are needed for local analysis. Day 1 samples will be analysed locally, all other samples may be analysed centrally.
- ⁴ If a urine sample is not able to be provided, a serum pregnancy test will be performed by a local laboratory.
- ⁵ Refer to Protocol Section 5.2.1.2 for directions and timing of PK sampling.
- ⁶ In addition to time points indicated, obtain a sample for ADA determination anytime subject experiences a moderate-to-severe IAR during the next study visit (≥ 4 days after the IAR) and prior to the infusion.
- ⁷ Lumbar puncture and MRI procedures may be performed under general anaesthesia or light sedation, as clinically appropriate in accordance with local institutional procedures. If clinically indicated, subjects may also receive general anaesthesia or sedation for central line placement for long-term vascular

access, in accordance with institutional guidelines. When possible, the procedure to place the central line should be performed while the subject is already anaesthetised or sedated for another study procedure. After the lumbar puncture is completed, the subject should be observed as per institution standard practice. Vital signs, adverse events, and concomitant medications should be assessed before the subject is discharged from the site.

- ⁸ During study visits where CSF is collected, and no serum chemistry sample is indicated per the SOA, a serum albumin sample should be collected to assess CSF-AI. After the lumbar puncture is completed, the subject should be observed as per institution standard practice.
- ⁹ A telephone follow-up call will be made 4 weeks after the last dose received of SBC-103 after Week 156 End of Treatment or after the Early Termination visit.
- ¹⁰ All AEs should be followed until they have returned to baseline values or stabilised or until the Investigator and Sponsor or designee agree that follow-up is no longer necessary.
- ¹¹ Information on all medications and treatments received by the subject within the 4 weeks preceding the Screening visit through the final visit will be recorded in the CRF.

Alexion Pharmaceuticals, Inc.

{Protocol: NGLU-CL01-T 24 Feb 2016 (Version 2.0 Final)}

Statistical Analysis Plan {01 Sep 2017, Version 1.0}

¹² Starting at Week 54, vital signs may be taken pre-dose (within approximately 30 minutes), approximately every 15 minutes during infusion and approximately every 15 minutes for 1 hour after completion of the infusion, provided there is no occurrence of IARs during the infusion. Vital signs will be obtained after any lumbar puncture as per site standard of care.

9.2. Changes from Analyses Specified in the Previous Version of the SAP

Not applicable.

9.3. Sample Size, Power, and Randomization

9.3.1. Sample Size and Power

The sample size of up to 5 subjects was determined by the number of subjects enrolled in the prior NGLU-CL01 study, based on clinical and not statistical considerations and is considered sufficient to provide PK, safety, and PD/efficacy data, which in combination with data from other NGLU studies could be used to inform dose selection, regimen, and study design for future studies.

9.3.2. Randomization

This is an open label, non-randomized study with no requirement for blinding.

9.4. Technical Specifications for Derived Variables

9.4.1. Baseline Definition

Baseline is defined as the value closest and prior to the first administration of SBC-103 on the first day of dosing. The first day of dosing is Day 0 in the Schedule of Assessments (SOA) and will be considered Relative Study Day 1 in order to construct CDISC compliant datasets. Analyses will use the assessments based on the Day 0 visit per the eCRF.

9.4.2. Visit Windows

It is expected that all visits will occur according to the protocol schedule. All data will be tabulated per the evaluation visit as recorded on the eCRF even if the assessment is outside of the visit window. In data listings, the relative day of all visits will also be presented.

9.4.3. Imputation of Partial Dates

For descriptive analysis purposes, partial dates will be imputed for some calculations (e.g. time to, and duration of, etc.). For calculation of time of laboratory test from diagnosis, partial dates will be handled as follows. Date of diagnosis must be imputed from age at diagnosis and date of birth (DOB). Date of diagnosis will be defined as DOB + age at diagnosis. If DOB contains partial dates, date of diagnosis will be defined as imputed DOB + age at diagnosis. Time from diagnosis will be calculated from imputed date of diagnosis.

For other analyses, partial dates will be handled by the following imputation methods:

• Imputations for ages (in months): If birthdate is not missing, Age = (Assessment date - birth date)/30.4375. If only birth year and month are available, Age = (Assessment year- birth year)*12 + (assessment month-birth month). If only birth year is available then a "midpoint date" of July 1 will be used for an imputed birth date; using July 1 of the birth year, Age = (Assessment date - imputed birth date)/30.4375. If the birth date is completely missing, Age = (age in years from eCRF*12) for Baseline (add the appropriate number of months for any follow-up assessments).

- AE Start Date Imputation: The earliest possible date will be imputed for start date of AEs. If the day of the month is missing, the day will be set to the first day of the month. If the day and month are both missing, the day and month will be assumed to be January 1.
- AE End Date Imputation: The latest possible date will be imputed for end date of AEs. If the day of the month is missing, the day will be set to the last day of the month. If the day and month are both missing, the day and month will be assumed to be December 31.
- Midpoint Imputation: For all other partial dates, a "midpoint date" will be imputed. If the day of the month is missing, the day will be set to the fifteenth (15th) day of the month. If the day and month are both missing, the day and month will be assumed to be July 1.
- Should the date created with these imputation rules place it outside the possible range of values established by complete, known dates (such as the birth date, death date, ICF date for study procedures), the closest known date will be used. In the case of date imputations for age calculations, the age as reported on the eCRF will be used as a reference to ensure the calculated age is appropriate.

For reporting purposes, a month will be defined as 30.4375 days (rounded and displayed to 1 decimal place) and a year defined as 365.25 days (rounded and displayed to 2 decimal places).

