7.2.2 Adverse Event Reporting Period

The study period during which AEs must be reported is defined as the period from signature of the informed consent to the end of the study treatment follow-up. AEs occurring after signing the informed consent but prior to the first dose of study medication will only be recorded if assessed as related to protocol procedures or requirements. For this study, the study treatment follow-up is defined as a minimum of 30 days following the last administration of study treatment. If a subject experiences an SAE that is considered to be related to study treatment at any time after the study, it must be reported to the Sponsor.

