5.2.1. Adverse Events (AEs)

Adverse events are defined in Protocol Section 7.1. Also refer to Appendix 9.4.3 of this SAP for special handling of AE partial dates. Any AE that occurs after the first dose of SBC-103 is considered a treatment emergent adverse event (TEAE) for this study.

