7.3.2. Adverse Events (AEs)

Information will be summarized on all AEs that began at any time from the date of first study procedure performed through the last procedure at the last study visit. Adverse events will be

classified by the study Investigator into one of the following relations to study drug: not related, unlikely related, possibly related or related to study drug. For reporting purposes, "related" events will include all AEs assessed by the Investigator as: possibly related or related to study drug.

All AEs captured in the eCRF will be coded using the Medical Dictionary for Regulatory Activities (MedDRA) coding system and displayed in tables and data listings using System Organ Class (SOC) and Preferred Term (PT). All AEs will be coded using the MedDRA, version 13.1 or higher.

Severity of AEs will be graded on a 3-point scale (mild, moderate and severe) based on the definitions, developed from Clinical Data Interchange Standards Consortium (CDISC) Study Data Tabulation Model (SDTM) standard terminology v3.1.1 (see Protocol Section 7.1.1).

Adverse event incidence will be reported based on the concept of treatment emergence for the purposes of this analysis. Any AE that occurs after the first dose of SBC-103 is considered a treatment emergent adverse event (TEAE) for this study.

Adverse events are summarized by patient incidence rates; therefore, in any tabulation, a patient contributes only once to the count for a given AE.

The number and percentage of patients with a TEAE will be summarized.

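### The partial-date rule for adverse event starts (SAP 9.4.3) has no first-dose check, so applied literally it can move post-dose events out of the treatment-emergent tables

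*SAP*

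**What the plan says.** SAP 9.4.3 imputes an incomplete AE start date to the earliest date the known parts allow. "If the day of the month is missing, the day will be set to the first day of the month"; with day and month both missing, 1 January is used. A range check then replaces any imputed date that falls outside the limits "established by complete, known dates (such as the birth date, death date, ICF date for study procedures"). The first-dose date is not among the named examples.

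SAP 5.2.1 refers to this appendix "of this SAP for special handling of AE partial dates", and its next sentence is the TEAE definition: "Any AE that occurs after the first dose of SBC-103 is considered a treatment emergent adverse event (TEAE) for this study". SAP 7.3.2 makes the tables depend on that flag: "Adverse event incidence will be reported based on the concept of treatment emergence".

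Two statements bear on scope. SAP 9.4.3 opens by saying that "partial dates will be imputed for some calculations (e.g. time to, and duration of, etc".), and then introduces the AE rules with "For other analyses, partial dates will be handled by the following imputation methods". On collection, Protocol 7.2.2 says that AEs arising after consent but "prior to the first dose of study medication will only be recorded if assessed as related to protocol procedures or requirements".

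**The concern.** Imputing an AE start as early as possible suits durations, but it works against a flag that asks whether the event began after first dose. An AE known only to have started in the month of first dose is sent to the 1st, which normally precedes dosing, and so fails the TEAE definition. Yet under Protocol 7.2.2 a recorded AE with no link to a study procedure or protocol requirement can only be post-dose. The SAP does not use that information.

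AE incidence is part of the primary safety endpoint. The report has been cut back to demographics, disposition, exposure and safety, and SAP 4.1.4 reduces laboratory, vital-sign, CSF and exposure data to listings. The TEAE and serious TEAE tables are therefore among the main tabulated results. An undercount there, or two programmers reaching different counts from the same SAP, matters more than it would in a fuller report.

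**Working it through.** The plan states no figure to reproduce, so the rule was applied to every possible first-dose date.

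**Inputs.** Imputation rule and range check: SAP 9.4.3. TEAE definition: SAP 5.2.1. Consent up to 90 days before screening: Protocol 5.1.1. Screening up to 28 days and last contact at Week 160: Protocol Appendix A. Up to 5 subjects: SAP 9.3.1. Assumptions: a 365-day year, each dosing date equally likely, and an AE that truly began on or after the dosing day.

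**Worked example (illustrative dates).** Consent 30 July, first dose 20 August.
- True onset 27 August, day missing: imputed to 1 August, before dosing, so not a TEAE.
- True onset 10 November, only the year known: imputed to 1 January, raised to 30 July by the ICF bound, still before dosing, so not a TEAE.

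**Share of dosing dates affected, if an imputed date equal to the dosing date counts as a TEAE.**
- Day missing: every date except the twelve that are the 1st of a month. 365 − 12 = 353; 353/365 = 96.7%.
- Day and month missing: every date except 1 January. 365 − 1 = 364; 364/365 = 99.7%.

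**Weighted by the days on which such an AE could start** (dosing day to end of month or year).
- Day missing: seven 31-day months, four 30-day months and one 28-day month give 7×496 + 4×465 + 406 = 5,738 eligible onset days. The 365 that belong to a first dose on the 1st are kept. (5,738 − 365)/5,738 = 5,373/5,738 = 93.6%.
- Day and month missing: 365×366/2 = 66,795 eligible days. (66,795 − 365)/66,795 = 66,430/66,795 = 99.5%.

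If the TEAE definition is read as requiring a calendar date strictly later than the dosing date, every such AE is lost in both cases.

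**Effect of the lower bound** (imputed date = later of the earliest date and the bound; same-day dates count).

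| Bound | Day missing | Day and month missing |
|---|---|---|
| ICF on dosing day | 0/365 | 0/365 |
| ICF 1, 28 or 118 days before dosing | 353/365 | 364/365 |
| First-dose date | 0/365 | 0/365 |

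The 118 days are the longest gap the protocol allows: 90 + 28.

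**Follow-up exposed.** The mean time from dosing to month end is 5,373/365 = 14.7 days, and to year end 364/2 = 182 days. Planned follow-up is 160 × 7 = 1,120 days, so the exposed part is 14.7/1,120 = 1.3% and 182/1,120 = 16.3%.

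**Effect on a table row.** One subject lost is 1/5 = 20 percentage points at N=5, 1/4 = 25 at N=4 and 1/3 = 33 at N=3, and only if the event is that subject's only one in the row.

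**The case against.** The best defence is that the SAP already allows the right answer. Its range check is mandatory and its list of bounds is open-ended. Read with Protocol 7.2.2, a pre-dose date is impossible for an AE unrelated to a procedure or protocol requirement, so a careful programmer would use first dose as the bound. In addition, no sentence says the TEAE flag uses the imputed date, and 9.4.3 opens by limiting imputation to some calculations. This stands as a limit on the claim but does not close the gap. The first-dose bound is permitted, not required. Procedure-related AEs may be recorded before dosing, so a pre-dose date is not automatically out of range. And 5.2.1 links the partial-date rule to the TEAE definition.

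The trigger is also improbable, and this stands. Protocol 7.3 requires start dates, with clock time for AEs within 24 hours of an infusion. The first weeks include in-patient monitoring, dosing visits every two weeks and calls after doses two to four. Year-only dates are unlikely.

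The percentages are calendar facts, not error rates for this trial; that is right. The 1,120 days are planned follow-up. Development was stopped on 11 July 2017 (SAP section 4) and actual follow-up is not given; if it was shorter, the exposed share is larger.

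Infusion-associated reactions (IARs) are barely touched. Their row in SAP 7.3.2.1 sits inside the TEAE summary, but they are timed by the clock around an infusion and summarised separately in 7.3.2.5.2.

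Finally, a misplaced event would be visible in the by-patient listings, and there is no inference to distort.

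**Conclusion.** The point holds, as a conditional one. Applied literally to the TEAE flag, SAP 9.4.3 gives a pre-dose start to almost any AE dated only to the first-dose month (353 of 365 dosing dates) or year (364 of 365), and no text requires a first-dose bound or a TEAE default. This rests on the imputed date being used for the flag, which 5.2.1 suggests but does not state, on consent preceding dosing by at least a day, and on such partial dates existing. Their number is unknown and may be zero. With at most 5 subjects, descriptive analysis and full listings, the practical effect is limited. It still concerns the tables for the primary safety endpoint, errs towards undercounting, and leaves the count to the programmer. It should be corrected.

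**What to change.** Add to SAP 9.4.3:

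> *If the known parts of an AE start date match the month and year of first dose (or, with the month missing, the year), the start date is set to the first-dose date and the AE is classed as a TEAE, unless its known end date is before first dose. Otherwise the earliest compatible date is used.*

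Stating the TEAE class outright matters, because a first-dose bound alone would still fail if same-day dates were not counted as after dosing.

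The cost is one sentence and one condition in the derivation code, using the AE start date, AE end date and first-dose date. The drawback is that a partially dated, procedure-related AE that truly preceded dosing, for example after the Day 0 lumbar puncture or anaesthesia, may be counted as a TEAE. That could shift a row by one subject in the other direction. It errs towards reporting more events, and it can be seen in the listings, which show each AE's relationship to study procedures (SAP 7.3.2.3).
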